6.4 EFFICACY ANALYSES

The analysis population for the efficacy analyses will consist of all randomized patients who provided informed consent (i.e., ITT population), with patients grouped according to their assigned treatment.

Efficacy analyses will be stratified by the randomization strata *and adjusted for mechanical thrombectomy planned status at baseline (Yes vs. No)*, unless otherwise noted. For the purpose of the primary efficacy analysis, patients with missing mRS scores at Day 90 will be imputed. Robustness of the primary analysis results will be explored by the tipping point approach, where departures from the missing at random (MAR) assumption will be assessed. Details of the imputation model and sensitivity analyses will be pre-specified in the SAP of the study.

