4.1 ANALYSIS POPULATIONS

4.1.1 Efficacy Analysis Population

All efficacy analyses will be based on the intent-to-treat (ITT) population, defined as all randomized patients who provided informed consent, and analyzed according to the treatment assignment at randomization.

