4.6.1 Primary Efficacy Endpoint

The primary endpoint is the ordinal mRS score at Day 90. mRS is an assessment of disability with values from 0 (no symptoms at all) to 5 (severe disability); death will be scored as a 6. During the study, mRS is collected at Baseline, Day 5 or hospital discharge, and 30 and 90 days after randomization. If death occurs prior to a scheduled assessment day, the mRS will be considered available and will be set to 6. The methodology for imputations related to the primary endpoint is described in Section [4.9.1.1](#).

The distribution of mRS at Day 90 will be summarized descriptively, and plotted using Grotta bars.

Analysis of the primary endpoint will test the hypothesis as follows:

$$H_0: OR_{\{TNK \text{ vs Placebo}\}} = 1 \text{ vs. } H_1: OR_{\{TNK \text{ vs Placebo}\}} \neq 1,$$

where $OR_{\{TNK \text{ vs Placebo}\}}$ stands for the overall odds ratio of achieving a lower level vs. higher level mRS between the tenecteplase and the placebo arms. Superiority of tenecteplase over placebo will be declared if the p-value of the estimated treatment effect is ≤ 0.003 (two-sided) at the efficacy interim analysis or ≤ 0.049 (two-sided) at the final analysis, after adjustment for one efficacy interim analysis.

In case there are issues with fitting the proportional odds model (such as e.g. a quasi-complete separation), the stratified Wilcoxon-Mann-Whitney Generalized Odds Ratio statistic (WMW GenOR) as described below will be employed. Otherwise, the proportional odds assumption will be tested. For this purpose, a proportional odds model will be fitted for the Day 90 mRS outcome, which will include treatment and adjusting variables. If the p-value for the overall score test of the proportional odds hypothesis is > 0.05 , the proportional odds assumption will be deemed acceptable. The assessment of the proportional odds assumption will be independent of the results from the primary efficacy analysis from the proportional odds model.

If the proportional odds hypothesis is not rejected, the parametric proportional odds model described above will be used to analyze the primary efficacy endpoint. The estimated common odds ratio of a lower mRS score (better outcome) will be presented for treatment (TNK vs. placebo). The corresponding Wald p-value and 95% CI will also be obtained.

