4.6.4 Sensitivity Analyses

4.6.4.1 Analysis Using Hypothetical Strategy for COVID-19 Intercurrent Events

The analysis of the primary efficacy endpoint will be repeated in the ITT population, applying the hypothetical strategy for COVID-19 intercurrent event. This will exclude any mRS data collected after being infected with COVID-19. Missing Day 90 mRS scores, including those being excluded due to COVID-19 intercurrent event, will be imputed according to the methodology described in Section 4.9.1.1. In case of non-existence of post-baseline mRS data after applying the hypothetical strategy, subject(s) will be

excluded from the analysis. In this analysis, treatment policy strategy will still be used for non-COVID-19 intercurrent event.

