4.9 MISSING DATA

Missing data will be maintained as missing in the analysis datasets, unless specified otherwise. For variables where missing data are imputed, the analysis dataset will contain a new record with the imputed value and the original variable value will be maintained as missing.

4.9.1 mRS

For patients with no post-baseline mRS assessments, missing post-baseline mRS scores will not be imputed and these patients will be excluded from all mRS related analyses.

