4.9.1.2 Multiple Imputation

Missing mRS data will be imputed using a sequential regression method. Particularly, mRS will be sampled from a multinomial distribution. This distribution will be estimated by ordinal logistic regressions, using baseline covariates and the previous mRS value.

The ordinal logistic regressions estimate the cumulative odds for achieving an mRS outcome of at most k :

$$\text{logit}[\Pr(mRS_t \leq k)] = \alpha_{kt} + X\beta_t + mRS_{t-1}\delta_t$$

where t is the time point index (Day 5, Day 30, Day 90), $k = 0$ to 5 , α_{kt} are intercepts, X is the design matrix for the baseline covariates and β_t are the corresponding regression coefficient vectors, and mRS_{t-1} is the previous mRS result (baseline, Day 5 or hospital discharge, or Day 30) with its coefficient δ_t . The list of covariates will include age, sex, race (white vs. non-white), baseline NIHSS, occlusion type and discharge destination (home vs. non-home).

Separate regressions will be fitted for each treatment group to avoid any assumptions about the treatment effect. In order to limit the number of parameters and prevent estimation issues, it will be assumed that the covariate effects β_t and δ_t do not depend on k (the proportional odds assumption). The model may be revised if estimation issues are encountered (e.g. quasi-complete separation). Logit is the usual link transformation, associated with a logistic regression.

For each fixed value of Δ , imputation is carried out in the following steps. These steps are repeated to impute missing mRS first at Day 30, then at Day 90 (using imputed Day 30 results):

- Fit the ordinal logistic regressions for mRS at time t , separately in the TNK and placebo groups.
- For patients with missing mRS at time point t , obtain the predicted cumulative probabilities. In the placebo group, use the probabilities predicted by the model. In the TNK group, recalculate the probabilities using the following equation.

$$\text{logit}[\Pr(mRS_t \leq k)] = \widehat{\alpha}_{kt} + X\widehat{\beta}_t + mRS_{t-1}\widehat{\delta}_t - \Delta$$

where $\widehat{\alpha}_{kt}$, $\widehat{\beta}_t$ and $\widehat{\delta}_t$ are the estimated coefficients from the TNK model. The penalty term Δ reduces the odds for a favorable outcome. This penalty will only be applied the first time mRS is missing for the patient; its effect will be propagated to subsequent time points by the mRS_{t-1} term in the regression.

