- Draw mRS at time t from the above distribution, with these additional considerations:
 - (a) Intermittently missing mRS cannot be imputed with mRS=6. Where mRS=6 is generated for imputation, mRS=5 will be imputed instead.
 - (b) Once mRS=6 is imputed, it will be propagated to all subsequent missing time points.

Note that by this algorithm, all ITT patients with baseline covariates will have Day 90 either observed or imputed. The process will be repeated to obtain 100 independent copies of the imputed dataset.

To analyze the multiply imputed data, apply the primary analysis model to each of the imputed dataset to arrive at 100 estimated treatment effects, $\gamma^{(m)}$ and their standard errors $S^{(m)}$, $m = 1$ to 100. The multiple imputation estimate and its standard error are then provided by the multiple imputation inference (SAS PROC MIANALYZE). The confidence interval and p-value can also be obtained from these estimates.

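### SAP 4.9.1 removes patients with no post-baseline mRS from the primary analysis, against the ITT definition, protocol 6.4 and SAP 4.9.1.2; the expected effect is small

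*SAP*

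**What the plan says.** On who is analysed:

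- SAP 4.1.1: "All efficacy analyses will be based on the intent-to-treat (ITT) population, defined as all randomized patients who provided informed consent".
- Protocol 6.4, on the primary analysis: "patients with missing mRS scores at Day 90 will be imputed". No exception is stated; the imputation model is left to the SAP.
- SAP 4.9.1, for patients with no post-baseline mRS: "missing post-baseline mRS scores will not be imputed and these patients will be excluded from all mRS related analyses".
- SAP 4.9.1.2, a subsection of the same section: "all ITT patients with baseline covariates will have Day 90 either observed or imputed".
- SAP 4.6.4.1 repeats the exclusion in the COVID-19 sensitivity analysis: "In case of non-existence of post-baseline mRS data after applying the hypothetical strategy, subject(s) will be" excluded.

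On deaths, SAP 4.6.1 says: "If death occurs prior to a scheduled assessment day, the mRS will be considered available and will be set to 6". SAP 4.9.1.1 likewise gives 6 to patients who die before the Day 90 visit. Other missing Day 90 scores are carried forward from Day 30 or Day 5/discharge.

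On the order of imputation, SAP 4.9.1.2 defines a "time point index (Day 5, Day 30, Day 90") but then imputes "first at Day 30, then at Day 90 (using imputed Day 30 results"). The code in Appendix 3 starts one step earlier, at Day 5. SAP 4.9.1.2 forbids a drawn score of 6 only for intermittent gaps.

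**The concern.** The superiority claim needs one prespecified patient set, and these passages give two. The set in SAP 4.9.1 also depends on outcome. A patient who dies before any assessment stays in with the worst score, while a patient not known to have died and never assessed drops out. Removing survivors raises the share of deaths in that arm, so the arm that loses more of them looks worse than it was.

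The rule covers every mRS analysis. That includes functional independence (SAP 4.6.2.1), the first secondary endpoint in the testing order, which reuses the primary imputations.

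**Working it through.** **Inputs.** SAP 2.3 and Table 1: Day 90 mRS 0-6 of 17/20/16/15/13/7/12% (tenecteplase) and 13/13/12/14/18/12/18% (placebo), 228 per arm, 5% dropout, 432 evaluable, two-sided 0.049 (z = 1.9686). Missing rates by arm are not in the documents and are assumed below.

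**1. The plan's own figure.** For Wilcoxon-Mann-Whitney with 216 per arm, P(tenecteplase better) + half the ties = 0.58955. With p̄ the mean of the two columns, Σp̄³ = 0.021616, so the null variance is (1/12)(2/216)(1 − 0.021616) = 0.000755. Power = Φ(0.08955/√0.000755 − 1.9686) = 90.2%. With a separate alternative variance it is 90.5%. By the proportional-odds formula, V = (432/12)(0.978384) = 35.22, and Φ(ln 1.76 × √35.22 − 1.9686) = 91.7%. The stated figure of at least 90% reproduces.

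**2. The texts side by side.**

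| Patient without a Day 90 mRS | SAP 4.9.1, 4.9.1.1, 4.6.1 | SAP 4.1.1 with protocol 6.4 | SAP 4.9.1.2, final note |
|---|---|---|---|
| Died before Day 90 | kept, 6 | kept | kept |
| Day 5/discharge or Day 30 score present | kept, carried forward | kept, imputed | kept, imputed |
| No post-baseline score, not known to have died | **removed** | kept, imputed | kept, imputed |

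The third row cannot be reconciled as written. A Day 30 start also fails to reach it, because there is no Day 5 value to predict from; the Appendix 3 order does reach it. However, Appendix 3 processes only records with complete covariates. One covariate, discharge destination, is not a baseline variable and may be unknown for a patient who withdrew in hospital.

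**3. Mechanism.** Under the null, with the placebo column in both arms, an arm has 0.18 × 228 = 41.04 deaths. Removing survivors equal to 2% of the arm (4.56 patients) leaves 223.44, and the death share becomes 41.04/223.44 = 18.37%.

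**4. Size.** These are unadjusted proportional-odds fits to expected counts, 228 per arm, with the removed patients a random sample of survivors within arm. False positives favouring tenecteplase = 1 − Φ(1.9686 − shift/SE). Power uses Table 1 with the loss reversed.

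| Removed, one arm/other arm | Null shift in log OR (placebo loses more) | SE | False positives | Power (tenecteplase loses more) |
|---|---|---|---|---|
| 0%/0% | 0 | 0.1641 | 2.45% | Φ(0.5563/0.1659 − 1.9686) = 91.7% |
| 1%/1% | 0 | 0.1649 | 2.45% | Φ(0.5568/0.1668 − 1.9686) = 91.5% |
| 0%/2% | +0.0113 | 0.1649 | 2.9% | Φ(0.5473/0.1667 − 1.9686) = 90.6% |
| 1%/3% | +0.0115 | 0.1657 | 2.9% | Φ(0.5477/0.1676 − 1.9686) = 90.3% |
| 0%/3% | +0.0171 | 0.1653 | 3.1% | Φ(0.5428/0.1671 − 1.9686) = 90.0% |

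The 91.7% in the first row is for all 456 patients under Table 1. It matches the formula value in step 1 only by coincidence.

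**5. Does imputing these patients cure it?** Drawn from the remaining arm, the 4.56 patients in step 3 receive 4.56 × 0.1837 = 0.84 deaths. The death share is then (41.04 + 0.84)/228 = 18.37%, unchanged. With draws limited to 0-5 it is 41.04/228 = 18.0%, the true value.

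A simulation (20,000 trials per scenario, Monte Carlo SE 0.11-0.17 points) agrees. For 0%/2%, 1%/3% and 0%/3% the false-positive rates were:

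- exclusion: 2.8%, 3.0%, 3.1%
- imputation as written: 2.8%, 2.9%, 3.0%
- draws limited to 0-5, half of these patients documented alive: 2.7% in each
- draws limited to 0-5, all documented alive: 2.5%, 2.6%, 2.4%

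The expected-count check in step 4 confirms only the exclusion figures.

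**The case against.** **The protocol leaves detail to the SAP, and the SAP uses ITT loosely.** Missing NIHSS items and assessments done by a mode not allowed are not imputed either (SAP 4.6, 4.6.2.5). So SAP 4.9.1 is an open, prespecified rule, and that stands. But protocol 6.4 delegates the imputation model, not the removal of patients, and SAP 4.9.1.2 says the opposite of SAP 4.9.1.

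**The Day 30 start fits the exclusion.** True: every patient left after SAP 4.9.1 has an earlier score or is scored 6. On that reading the outliers are the note in 4.9.1.2 and Appendix 3, which serve only the tipping-point analysis. The conflict with SAP 4.1.1 and protocol 6.4 remains.

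**Few patients are affected.** This stands. The first post-baseline score is due at discharge or Day 5, mRS may be taken by telephone (protocol 4.5.4), and a double-blind trial gives little reason to expect imbalance. The shifts in step 4 are about 0.1 of a standard error or less.

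Four stronger readings are tempting, and the documents do not support them.

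- *Early deaths are removed too.* SAP 4.9.1 read alone might suggest it, but SAP 4.6.1 counts them as available.
- *LOCF is itself an error.* It is an imputation, which is what protocol 6.4 asks for. Whether it biases depends on recovery after the carried score, and the documents give no data on that. LOCF against multiple imputation as primary is a trade-off.
- *The tipping point is defective because it starts from multiple imputation under MAR.* Protocol 6.4 sets its purpose as departures from MAR, and SAP 4.6.4.3 requires a plot of p against delta whenever p exceeds alpha for some delta, which includes zero.
- *The exclusion could overturn the trial.* Adding back 12 patients per arm to 216, all tenecteplase at 6 and all placebo at 0, takes the odds ratio from 1.74 to 1.26 (p = 0.16). That is an extreme bound; nothing suggests such a pattern. With both sets at 5, the odds ratio is 1.69 (p = 0.0016).

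**Conclusion.** Wrong as written, with a small expected effect. The contradiction and the outcome-dependent selection follow from the text alone. So do the two linked faults: the differing start of imputation, and a drawn score of 6 being possible for a patient known to be alive at Day 90.

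The size rests on assumed rates, on the removed patients being survivors missing at random within arm, and on an unadjusted model where the plan's is adjusted. Balanced loss gives no bias. If some of the removed patients had in fact died, the bias would be smaller than shown.

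**What to change.** (a) Delete the exclusion in SAP 4.9.1 and 4.6.4.1. Impute these patients by SAP 4.9.1.2 at delta = 0, keep LOCF for all others, combine by Rubin's rules, and report their number by arm. Run the proportional-odds test once, on observed and carried scores, and apply its choice to every imputed dataset.

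(b) Align SAP 4.9.1.2 with Appendix 3: Day 5/discharge, then Day 30, then Day 90. State how a missing discharge destination is coded.

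(c) Limit draws to 0-5 for patients documented alive at Day 90, using the vital status already needed for the Day 90 mortality and survival endpoints (SAP 4.8.2.3, 4.6.3.8). Without (c), (a) settles the patient set but removes little of the bias.

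(d) As a reporting addition, show the delta = 0 estimate beside the LOCF primary. The two differ in imputation method and can fall on opposite sides of alpha. A simulation under assumed recovery patterns, not independently confirmed, put this at 1.6% of trials with 5% dropout in each arm.

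Cost: modest programming and a slightly more complex primary analysis, with no change to sample size. Withdrawn consent may limit (c). If the interim look at 0.003 has already been run with the exclusion, document how many patients it removed.

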4.9.1.1 Last Observation Carried Forward

For patients who died prior to completing the Day 90 study visit, the missing mRS score at Day 90 will be imputed as 6. Otherwise, missing mRS data at Day 90 will be imputed using a LOCF technique, where the missing mRS score at Day 90 will be imputed by the

last observed mRS score, Day 30 or Day 5 / hospital discharge mRS value but not the baseline value.

4.9.1.2 Multiple Imputation

Missing mRS data will be imputed using a sequential regression method. Particularly, mRS will be sampled from a multinomial distribution. This distribution will be estimated by ordinal logistic regressions, using baseline covariates and the previous mRS value.

The ordinal logistic regressions estimate the cumulative odds for achieving an mRS outcome of at most k :

$$\text{logit}[\Pr(mRS_t \leq k)] = \alpha_{kt} + X\beta_t + mRS_{t-1}\delta_t$$

where t is the time point index (Day 5, Day 30, Day 90), $k = 0$ to 5 , α_{kt} are intercepts, X is the design matrix for the baseline covariates and β_t are the corresponding regression coefficient vectors, and mRS_{t-1} is the previous mRS result (baseline, Day 5 or hospital discharge, or Day 30) with its coefficient δ_t . The list of covariates will include age, sex, race (white vs. non-white), baseline NIHSS, occlusion type and discharge destination (home vs. non-home).

Separate regressions will be fitted for each treatment group to avoid any assumptions about the treatment effect. In order to limit the number of parameters and prevent estimation issues, it will be assumed that the covariate effects β_t and δ_t do not depend on k (the proportional odds assumption). The model may be revised if estimation issues are encountered (e.g. quasi-complete separation). Logit is the usual link transformation, associated with a logistic regression.

For each fixed value of Δ , imputation is carried out in the following steps. These steps are repeated to impute missing mRS first at Day 30, then at Day 90 (using imputed Day 30 results):

- Fit the ordinal logistic regressions for mRS at time t , separately in the TNK and placebo groups.
- For patients with missing mRS at time point t , obtain the predicted cumulative probabilities. In the placebo group, use the probabilities predicted by the model. In the TNK group, recalculate the probabilities using the following equation.

$$\text{logit}[\Pr(mRS_t \leq k)] = \widehat{\alpha}_{kt} + X\widehat{\beta}_t + mRS_{t-1}\widehat{\delta}_t - \Delta$$

where $\widehat{\alpha}_{kt}$, $\widehat{\beta}_t$ and $\widehat{\delta}_t$ are the estimated coefficients from the TNK model. The penalty term Δ reduces the odds for a favorable outcome. This penalty will only be applied the first time mRS is missing for the patient; its effect will be propagated to subsequent time points by the mRS_{t-1} term in the regression.

- Draw mRS at time t from the above distribution, with these additional considerations:
 - (a) Intermittently missing mRS cannot be imputed with mRS=6. Where mRS=6 is generated for imputation, mRS=5 will be imputed instead.
 - (b) Once mRS=6 is imputed, it will be propagated to all subsequent missing time points.

Note that by this algorithm, all ITT patients with baseline covariates will have Day 90 either observed or imputed. The process will be repeated to obtain 100 independent copies of the imputed dataset.

To analyze the multiply imputed data, apply the primary analysis model to each of the imputed dataset to arrive at 100 estimated treatment effects, $\gamma^{(m)}$ and their standard errors $S^{(m)}$, $m = 1$ to 100. The multiple imputation estimate and its standard error are then provided by the multiple imputation inference (SAS PROC MIANALYZE). The confidence interval and p-value can also be obtained from these estimates.

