hr=hour; MT=mechanical thrombectomy; PBO=placebo; R=randomized; TNK=tenecteplase.

Note: The primary endpoint will be assessed at the Day 90 visit.

Appendix 3

SAS Code for Statistical Analysis

Analysis	Sample Code
Ordinal mRS parametric analysis and the test for proportional odds	<pre>proc logistic; class trt x1-x4; model Y = trt x1-x4; run;</pre> 
where Y is the ordinal mRS score, trt is treatment, and x1-x4 are randomization stratification factors. The score test for proportional odds is generated by default.

Multiple imputations for the tipping point analysis, ordinal mRS	
I. Obtain prediction probabilities for mRS at time point t.
 <pre>proc logistic; by trt; ... model Yt = ... Yp; output out=fit predicted=p; run;</pre> 
where Yt is the ordinal mRS score at time t, trt is treatment group, Yp is the value of mRS at the previous visit.
 
II. Apply the penalty to the predicted probabilities.
 <pre>data fit; set fit; if not missing(p) then do; oddsr=p/(1-p); newoddsr=oddsr/delta; newp=newoddsr/(1+newoddsr); end; run;</pre> 
III. Replace missing values of mRS at time t with random draws from the multinomial distribution defined by the vector of cumulative probabilities p or newp. newp is used for the values in the TNK group to impute for the first missing time point; other imputations will use p.
 <pre>data outmi; ...</pre>

	<pre> x=rand('TABLE',p0,p1-p0,p2-p1,p3- p2,p4-p3,p5-p4)-1; ... run; </pre> 
The code will be executed first to impute Day 5 mRS, then Day 30 mRS, and then again to impute Day 90 mRS. Each time only the records with non-missing covariates and previous mRS value will be supplied.

Rubin's rules for the tipping point analysis, ordinal mRS (assuming proportional odds)	<pre> proc logistic data=outmi; model Y = trt x1-x4; by _Imputation_; ods output ParameterEstimates=PE; run; proc mianalyze parms=PE; modeleffects trt; run; </pre> 
where Y is the ordinal mRS score, trt is treatment, x1-x4 are randomization stratification factors, outmi is the dataset with multiple imputations, and _imputation_ is the index of the imputed dataset.

Wilcoxon-Mann-Whitney Generalized odds ratio	Derived through programming the formulas shown in Appendix 4 in data steps.

Appendix 4

Wilcoxon-Mann-Whitney Generalized odds Ratio

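### The tipping-point imputation models are fitted with patients already dead at the previous visit and drawn from fixed coefficients: survivors' deaths are overstated and Rubin's rules are not strictly met, with negligible effect on the treatment comparison

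*SAP*

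**What the plan says.** The tipping-point analysis (SAP 4.6.4.3) is the planned robustness check on the primary result. It rests on the sequential imputation in SAP 4.9.1.2, with SAS steps in Appendix 3.

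- **Who is in the fit.** "Fit the ordinal logistic regressions for mRS at time t , separately in the TNK and placebo groups". Appendix 3 adds: "Each time only the records with non-missing covariates and previous mRS value will be supplied". SAP 4.6.1 fixes the status of the dead: "If death occurs prior to a scheduled assessment day, the mRS will be considered available and will be set to 6". A score of 6 is non-missing, so it passes that filter.
- **How earlier mRS enters.** The regressor, SAP 4.9.1.2 explains, "is the previous mRS result (baseline, Day 5 or hospital discharge, or Day 30) with its coefficient". That is a single linear term, and its effect is assumed the same at every cut-point.
- **What is drawn from.** The values used for tenecteplase patients "are the estimated coefficients from the TNK model"; placebo patients use their own model's predictions. In Appendix 3 the probabilities come from "output out=fit predicted=p" and then feed a random table draw.
- **How it is combined.** "The process will be repeated to obtain 100 independent copies of the imputed dataset". Rubin's rules follow, through PROC MIANALYZE.

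Two further rules in 4.9.1.2 concern death: an intermittent gap may not be filled with 6, and an imputed 6 is carried forward. Both act on drawn values and leave the fit unchanged. The clause that lets the model be revised covers estimation problems only.

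**The concern.** A patient whose Day-90 mRS is imputed was not known to be dead at Day 30, because known deaths are scored 6. The relevant transitions are therefore those of survivors. Patients dead at Day 30 stay at 6 with certainty, and a logistic model with one linear slope cannot reproduce that certainty. It steepens the slope and still gives the dead some chance of a score below 6. The deaths it fails to assign to the dead are assigned to the living. Delta = 0 then does not represent missing at random among survivors, although 4.6.4.3 uses it as that reference point. The same applies to the Day-30 model and patients dead by the Day-5 or discharge assessment.

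The second issue is separate. Rubin's rules assume that each imputed dataset reflects uncertainty in the imputation parameters. Here 100 sets of draws share one set of estimates, so the between-imputation variance omits that part.

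At stake is the calibration of a sensitivity analysis, not the primary test.

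**Working it through.** **The plan's own figure.** The SAP states no expected number of imputed deaths and no imputation standard error. Its related stated figure is power of at least 90% with 432 evaluable patients at two-sided 0.049 (SAP 2.3), and the Table 1 distributions used below reproduce it.
- Wilcoxon-Mann-Whitney: P(better) + 0.5 P(tie) = 0.58955. The average category proportions give a sum of cubes of 0.0216, so the null SE = sqrt[(1 − 0.0216)/12 × 2/216] = 0.02748. Then 0.08955/0.02748 − 1.969 = 1.29, or 90.2% power.
- Proportional-odds formula: ln(1.76) × sqrt[432/12 × (1 − 0.0216)] − 1.969 = 1.39, or 91.7%.

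**Assumed inputs.** The documents give no Day-30 distribution. Assumed are the Day-30 to Day-90 transitions, the share f of Day-90 deaths already dead at Day 30, and data missing at random among patients alive at Day 30.

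**Why the deaths move.** Let D be an arm's Day-90 death proportion and q the fitted probability of mRS 6 at Day 90 for a patient dead at Day 30 (the truth is q = 1). If the fit roughly reproduces total deaths, survivors are assigned D − qfD instead of (1 − f)D. The overstatement is about

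R = (1 − qf)/(1 − f) = 1 + (1 − q) f/(1 − f).

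Large-sample fits with Table 1 outcomes gave q between 0.80 and 0.88.

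| f | R from formula, q = 0.88 to 0.80 | R from fitted model |
|---|---|---|
| 0.50 | 1.12 to 1.20 | 1.09 to 1.11 |
| 0.67 | 1.24 to 1.41 | 1.26 to 1.29 |
| 0.80 | 1.48 to 1.80 | 1.60 to 1.70 |
| 0.90 | 2.08 to 2.80 | 2.50 to 2.76 |

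Fitted without the Day-30 deaths, the ratio to the true rate is about 0.92 to 1.00.

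A second set of transitions (latent correlation 0.85) gives predicted against true death among survivors as follows.
- f = 0.65: 7.3% against 4.7% (tenecteplase) and 11.4% against 7.0% (placebo), ratios 1.6 and 1.6.
- f = 0.85: 5.8% against 2.1% and 9.2% against 3.1%, ratios 2.8 and 3.0. The last lies just above the 1.1 to 2.8 quoted as the rough range.
- Fitted on survivors only: 4.9%, 7.1%, 2.2% and 3.2%.
- The tenecteplase slope at f = 0.65 is −1.43 with the dead and −1.30 without.

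**In patients.** 5% of 456 is about 23 missing. At f = 0.67 the true survivor death rates are 0.12 × 0.33/(1 − 0.67 × 0.12) = 4.3% and 0.18 × 0.33/(1 − 0.67 × 0.18) = 6.8%, so about 1.2 deaths are expected. Simulated imputed deaths over both arms, plan against corrected fit:
- Previous mRS as the only covariate: 1.57 against 1.20 (f = 0.67) and 1.08 against 0.40 (f = 0.9), an excess of 0.4 and 0.7.
- Five covariates plus previous mRS: about 2.2 against 1.3 (65% of deaths early) and 1.8 against 0.7 (85%), an excess of 0.9 and 1.1, or up to 1.2 allowing for rounding.

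**Standard error.** Total variance = W + (1 + 1/100)B. At 5% missing and f = 0.67 the Rubin SE is 0.1665, so the total is 0.0277, with B = 0.0002: under 1% of the variance. Even doubling B would raise the SE by only about 0.0002/(2 × 0.0277) = 0.4%. With previous mRS as the only covariate, the ratio of fixed-estimate to bootstrap SE was 0.9999 at 5% missing, 0.9994 at 10% and 0.9964 at 20%. With five covariates added, the shortfall against the full fix was about 0 to 0.1% at 5% and 0.3 to 0.5% at 10%.

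**Treatment effect.** At 5% missing and f = 0.67 the mean log odds ratio was 0.5487 under the plan and 0.5489 after both changes. Across the checks, including Delta above 0, the difference was about 0.005 or less.

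**The case against.** The strongest reply is immateriality. The primary analysis carries the last mRS forward with death scored 6 (SAP 4.9.1.1) and never uses this model. At 5% dropout the excess is around one imputed death, in both arms, and the treatment estimate barely moves. All of that stands.

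The size also rests on assumed transitions, and two readings would shrink it. Discharge destination is an imputation covariate, and the documents do not say how it is recorded for patients who die before discharge. If it is missing, the Appendix 3 filter would drop those early deaths from the fit. The code is also sample code with elided statements; with previous mRS as a class variable the bias would largely vanish. Neither reading is written down, and 4.9.1.2 specifies one coefficient.

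A reader might infer that the reported tipping point is too favourable. One set of simulations (40 significant trials per scenario) found mean tipping values of 3.60 against 3.50, 2.49 against 2.44, 2.85 against 2.76 and 4.07 against 4.03, plan against corrected. These differ by 1 to 3% of Delta under a single assumed model, while other checks at fixed Delta found log odds ratio shifts within simulation error. The direction is not established, and such a shift would not alter the reading of a p-value plot.

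**Conclusion.** The point holds as a defect of specification in a sensitivity analysis. As written, the Delta = 0 model overstates death among patients alive at the previous visit, and the draws are improper for the combining rule that the SAP names. Both follow from the text; the sizes rest on assumed early-death shares of 0.5 to 0.9 and assumed transitions. The overstatement grows with the share of early deaths, and its count in patients grows with missingness.

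Two stronger readings are not supported. One is that the confidence intervals are materially too narrow: the shortfall is at most about 0.5% at twice the planned missingness. The other is that the imputation model is deficient because thrombectomy planned, randomization site and protocol version are absent. SAP 4.9.1.2 says "The list of covariates will include age, sex, race (white vs. non-white), baseline NIHSS, occlusion type and discharge destination", so age, severity and occlusion type are covered; Appendix 5 may itself remove the omitted variables from the analysis model, and no effect of leaving them out has been shown.

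**What to change.** In SAP 4.9.1.2 and Appendix 3:

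1. State that each visit's imputation model is fitted only in patients whose previous mRS is below 6.
2. For each of the 100 imputations, draw the coefficients from their estimated distribution before drawing mRS. Alternatively, refit on a bootstrap sample taken within each arm, with a stated fallback if estimation fails.

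The cost is a filter statement, a loop and more run time. Standard errors become marginally larger. A seven-level model with several covariates in about 200 patients per arm, fewer once earlier deaths are removed, will occasionally fail to estimate in a bootstrap sample, which is why the fallback is needed. The primary analysis and the alpha allocation do not change.
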